5.0 STUDY DESIGN

5.1 Figure 1: Overview: Study Activities

We will use a Hybrid Type 3 Effectiveness-Implementation design⁹ and a modified stepped wedge design^{1-4,10} to evaluate the effect of the IF on ED-initiated BUP with referral for ongoing MAT and its effectiveness. A Hybrid Type 3 design is recommended when there is strong face validity and strong initial evidence for the clinical and implementation interventions that would support generalizability; there is strong “implementation momentum” for adoption of the clinical intervention and evidence that the intervention being tested is feasible and supportable. In light of our prior work and the emphasis nationally on addressing the opioid epidemic, a Hybrid Type 3 design is warranted. The advantages of this design include a balanced provision of resources and support across all study sites, enrollment of comparable cohorts of participants during baseline evaluation and IF evaluation phases across all sites, and the completion of the proposed study in a short period of time (48 months). This overall short study time will minimize the potential impact of population related time trends and other time related factors such as changes in healthcare practice and policy. The randomized order of the timing of the IF at each site, offset by 3 month increments, is used to accommodate logistical constraints of a simultaneous implementation at all sites. The stepped wedge design is increasingly used to promote the implementation of evidence-based practice and is appropriate for evaluating interventions when there is evidence that the intervention is likely to be beneficial and when practical considerations require a sequential deployment of an intervention.^{4,10} At each of the four study sites, there will be a 12-month baseline evaluation period after the standard dissemination activity via a “grand rounds” education session, followed by a 6-month IF phase, followed by a 12-month IF evaluation period. A 6-month IF phase is required to allow adequate time to conduct the multiple components of the IF (see Table 1). An evaluation period of 12 months is necessary to enroll enough patients for adequate sample size. The number of patients should be similar during the baseline evaluation and the IF evaluation periods. The strategies included in the IF are iterative and continue throughout the IF and IF evaluation periods. The proportion of eligible study participants in each time period who are engaged in formal addiction treatment on the 30th day post enrollment will be assessed within each site and for the entire study cohort.

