11.3 Quantitative Data Collection and Analysis

The ORCA¹¹ instrument is based on the PARIHS framework, to evaluate evidence, context and facilitation-related factors impacting implementation ED-initiated BUP and referral for ongoing MAT. The ORCA has been applied to the evaluation of interventions intended to promote evidence-based practices, including addiction treatment, and predicts implementation efforts.³⁶⁻³⁸ Baseline ORCA, and provider readiness and preparedness scores will be used to determine evidence and context related strengths and weaknesses in organizational readiness to implement BUP and referral and to tailor the IF. Other process measurements will include the number of ED providers attending the initial educational session, participating in the BUP training courses, obtaining a DATA 2000 waiver, proportion of eligible patients receiving ED-initiated BUP, provider skill and adherence to critical actions on initiating BUP treatment with referral to ongoing MAT; and organization data including integration of materials into EHR and proportion of patients with ED-initiated BUP who are successfully linked to office-based BUP providers and/or OTPs. EHRs will be queried for each enrolling shift to determine potential ICD 10 codes identifying patients that were potentially eligible for ED-initiated treatment and/or referral.

ED Organizational Readiness: We will use the ORCA with wording to reflect ED-initiated BUP to measure factors impacting the rates of ED-initiated BUP. This 5-minute survey is based on the PARIHS framework and asks the respondent to rate local factors related to evidence, context and facilitation on a 5-point Likert scale from strongly disagree to strongly agree. Facilitation questions will be omitted from the baseline assessment since this part of the intervention will not have taken place.

Community Providers Organizational Readiness: We will use the ORCA to measure factors impacting the care of the study participants with ED-initiated BUP. This asks the respondent to rate local factors related to evidence, context and facilitation on a 5-point Likert scale from strongly disagree to strongly agree. Facilitation questions will be omitted from the baseline assessment since this part of the intervention will not have taken place.

ED Provider Readiness and Preparedness: We will use change rulers, among appropriate providers, to assess readiness and preparedness to provide ED-initiated BUP.³⁹ Stage of change

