3.3.6 Calendar Time

Calendar time for analysis is defined as the number of days since the site opened for enrollment in the baseline evaluation period. Below are the start and end dates for each site in each evaluation period. The start date is defined as the date the site was given access to the eClinical system to begin enrolling participants in the study for that particular evaluation period. The end date is defined as the last day the site was able to enroll participants in the EDC system for each evaluation period. Note that during the IFEP, enrollment was paused due to the COVID-19 public health measures put into place at two sites, Harborview Medical Center and University of Cincinnati. The days enrollment was paused will be considered as part of the primary analysis and several sensitivity analyses will be performed to account for this pause.

Site	Baseline Evaluation Period		IF Evaluation Period			
	Start Date	End Date	Start Date	Date Paused for COVID-19	Date Reopened for COVID-19	End Date
MA Johns Hopkins ED	4/10/2017	4/9/2018	10/9/2018	N/A	N/A	10/8/2019
NY Mount Sinai ED/Beth Israel	7/6/2017	7/5/2018	1/4/2019	N/A	N/A	1/5/2020
OV University of Cincinnati ED	10/9/2017	10/8/2018	4/8/2019	03/13/2020	6/10/2020	7/6/2020
PNW Harborview Medical Center ED	1/2/2018	1/1/2019	7/2/2019	03/3/2020	6/6/2020	10/4/2020

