
We will use appropriate non-parametric, parametric, and analysis of variance statistical procedures to descriptively evaluate the key characteristics of each study site (e.g., patient flow indicators such as length of stay of treated and released patients, and demographic and drug use characteristics of patients with OUD presenting at each ED site, indicators of organizational level differences between the sites (e.g., the number ED providers, number/ratio ED providers DEA waivered to prescribe BUP), and to evaluate comparability of baseline characteristics among patient cohorts enrolled at each of the study sites and overall during baseline evaluation period and the IF evaluation periods across all sites.

The EHR-abstracted data regarding MOUD activities in the ED will be summarized by site at the following time points separately: (1) the entire BEP; and (2) the entire IFEP. Exploratory analyses may evaluate whether any of the measures in this dataset are associated with primary implementation factors.

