IFEP	N	X.x	X.xx; X.xx
Sex			
Male	N	[ref]	[ref]
Female	N		
Race			
White	N	[ref]	[ref]
Black/African American	N		
Other	N		
Ethnicity			
Not Hispanic/Latino	N	[ref]	[ref]
Hispanic/Latino	N		
Sex-by-study phase interaction ²			
Male	N	X.x	X.xx; X.xx
Female	N	X.x	X.xx; X.xx
Race-by-study phase interaction ²			
White	N	X.x	X.xx; X.xx
Black	N	X.x	X.xx; X.xx
Other	N	X.x	X.xx; X.xx
Ethnicity-by-study phase interaction ²			
Not Hispanic/Latino	N	X.x	X.xx; X.xx
Hispanic/Latino	N	X.x	X.xx; X.xx

¹ Note that only covariates which remained in the final covariate-adjusted model will be included in this table.

² Coefficient and corresponding credible intervals are presented for the intervention effect in a particular subgroup (e.g., males).

Table 20: Summary of MOUD Practices by Site Over Time from EHR-abstracted Data

	Baseline Evaluation Period					IF Evaluation Period				
	MA Johns Hopkins ED	GNY Mount Sinai ED	OV University of Cincinnati ED	PNW Harborview Medical Center ED	Total	MA Johns Hopkins ED	GNY Mount Sinai ED	OV University of Cincinnati ED	PNW Harborview Medical Center ED	Total
Buprenorphine										
Administered	N									
Prescribed	N									
Administered and prescribed	N									
Unique providers administering or prescribing	N									
Naloxone										
Dispensed	N									
Prescribed	N									
Dispensed and prescribed	N									
Unique providers dispensing or prescribing	N									
X-waiver										
Physicians	N									
APPs	N									
Additional staff (counselors/peers)	N									

Table 21: COVID-19 Sensitivity Analyses Results for Primary Implementation Outcome

Sensitivity Analysis	GLMM		Bayesian Analysis		
	Intervention Coefficient	p-value	Risk Difference Estimation Time Point	Risk Difference	95% Credible Interval
Pre-COVID data	X.xx	x.xxx	Mid-point (day 632)	X.xx	X.xx; X.xx
			COVID-19 Pause (day 1423)	X.xx	X.xx; X.xx
COVID pause removed	X.xx	x.xxx	Mid-point (day 632)	X.xx	X.xx; X.xx
			COVID-19 Pause (day 1423)	X.xx	X.xx; X.xx

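### Table 20 compares raw department-wide BUP and naloxone counts over windows that, read literally, run 456 and 461 days against 365 at two sites, so unchanged practice could show a rise of anywhere from about 0% to 26% there

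*SAP*

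**What the plan says.** SAP 2.3.1.5 has sites abstract four items from their records: BUP prescribing or administration, BUP waivers among staff, naloxone prescribing or dispensing, and providers prescribing naloxone. None is a count of ED visits, of patients with OUD or of eligible patients. SAP 7.7 then states that these data "will be summarized by site at the following time points separately: (1) the entire BEP; and (2) the entire IFEP". It adds that exploratory analyses may look at associations with the implementation measures.

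The Table 20 shell is in SAP 16.1.3, with the primary implementation outcome. Its rows cover BUP administered, prescribed or both, naloxone dispensed, prescribed or both, provider counts such as "Unique providers administering or prescribing", and X-waiver headcounts. Each half has four site columns and a Total, and the cells show N alone. Tables 13 and 14, for the enrolled sample, carry a header N and a percentage.

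SAP 3.3.6 ends each period on the last day the site could enrol, and notes that "during the IFEP, enrollment was paused due to the COVID-19 public health measures put into place at two sites". The COVID-19 sensitivity analyses in SAP 7.5.2 cover only the two primary outcomes.

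**The concern.** A count depends on how long one counts. Table 20 puts two halves side by side and invites a before/after reading, yet at two of the four sites the second half spans about three more calendar months. What paused was enrolment. The abstracted data describe the whole department and do not depend on a patient consenting, so a literal reading of the whole IFEP includes the pause.

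At stake is whether growth in Table 20 can be read as a change in practice. The revised SAP text reports almost no overlap between the two periods and drops time from the model, so a supporting before/after table should at least have comparable windows. If the raw counts were used in the exploratory association analyses, the window difference would go with them, concentrated in two sites.

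**Working it through.** **Inputs.** Start, pause, reopening and end dates from the SAP 3.3.6 table. Period length = end − start + 1. Pause = reopening date − pause date, which counts the reopening day as open.

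**The plan's own figures first.** Protocol 5.1 says "there will be a 12-month baseline evaluation period" and later "followed by a 6-month IF phase, followed by a 12-month IF evaluation period". The BEP reproduces this at every site (365 days). The IFEP reproduces it in days open to enrolment: 365, 367, 456 − 89 = 367, and 461 − 95 = 366. The pauses, 89 and 95 days (2.9 and 3.1 months at 30.44 days per month), agree with the three-month delay described in SAP 7.5.2. Only the start-to-end span at the two paused sites departs from 12 months.

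**Expected count ratio with unchanged practice.** At a constant daily event rate, IFEP count / BEP count = days counted in the IFEP / days counted in the BEP.

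| Site | BEP days | IFEP days, start to end | Pause days | Ratio, pause counted at usual activity | Ratio, half activity in pause (assumption) | Ratio, pause left out |
|---|---|---|---|---|---|---|
| Johns Hopkins | 365 | 365 | 0 | 1.000 | 1.000 | 1.000 |
| Mount Sinai | 365 | 367 | 0 | 1.005 | 1.005 | 1.005 |
| Cincinnati | 365 | 456 | 89 | 456/365 = 1.249 | (367 + 44.5)/365 = 1.127 | 367/365 = 1.005 |
| Harborview | 365 | 461 | 95 | 461/365 = 1.263 | (366 + 47.5)/365 = 1.133 | 366/365 = 1.003 |
| Total, equal site volumes (assumption) | 1,460 | 1,649 | 184 | 1,649/1,460 = 1.129 | 1,557/1,460 = 1.066 | 1,465/1,460 = 1.003 |

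The documents give no ED volumes, so the activity level in the pause has to be assumed. No activity at all gives the same counts as leaving the pause out.

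**Effect of a per-time rate.** If N = rate × days, then 30 × N / days = 30 × rate in both periods, and every ratio returns to 1.00. This needs a divisor that matches the days abstracted. It also does not remove a change in ED volume: with half activity in the pause and all days counted, the rate would read 411.5/456 = 0.90 of baseline at Cincinnati and 413.5/461 = 0.90 at Harborview.

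**Which rows.** The ratios apply to event counts. A unique-provider count grows less than in proportion to time, because the same providers recur. An X-waiver headcount need not grow with time at all.

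**The case against.** The strongest reply is that the inflation is uncertain. SAP 2.3.1.5 says only that abstraction covered various timepoints; it does not say that pause days were included, and ED activity from March to June 2020 may have been well below usual. A reader might infer that counts at these sites do rise by a quarter with no change in practice. The documents do not support that: it is the top of a range that starts near zero. This part of the objection stands, and the size is given as a range for that reason.

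A reader might also infer that Table 20 is the plan's one check on whether the enrolled-sample result holds across the department. The SAP gives it no such role and attaches no test to it. Protocol 11.3 and SAP 2.3.1.2 list the proportion of eligible patients receiving ED-initiated BUP as a process measure, and SAP 15.0 lists only the tables that the data centre provides, so other summaries may exist. That stands too, but it does not make Table 20 itself readable.

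Third, the dates are printed and the table is split by site, so a careful reader could rescale. Two sites are free of the problem, and the hypothesised changes in protocol Table 4 (5% or 15% to 25%, a factor of 5 or 1.7) exceed 1.26. This limits the consequence. It does not remove it: rescaling requires knowing whether pause days were abstracted, which the SAP does not say, and those hypothesised changes concern enrolled patients rather than department counts.

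Last, the protocol plans that "EHRs will be queried for each enrolling shift to determine potential ICD 10 codes identifying patients that were potentially eligible", which looks like a ready denominator. Those queries follow enrolling shifts, so they would not cover other hours or the pause. An eligible-patient denominator is therefore not a cheap default.

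**Conclusion.** As written, Table 20 compares event counts over unequal windows at Cincinnati and Harborview and does not say so. With unchanged practice the apparent rise there is 25-26% if pause days were abstracted and activity was usual, about 13% if activity halved, and 0.3-0.5% if pause days were left out. The Total column rises by up to about 13% if site volumes are equal. The date arithmetic is firm; abstraction of pause days, activity during the pause and equal site volumes are assumptions that the documents neither confirm nor rule out.

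The point is limited to the BUP and naloxone event rows of a descriptive, exploratory table. It would be wrong to carry it over to the primary implementation result, which is defined on enrolled patients with its own denominator and is untouched. The change is worth making because it is cheap and removes a real ambiguity.

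**What to change.** In SAP 7.7 and the Table 20 shell:

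- Print the observation days for each site and period.
- State whether the 89 pause days at Cincinnati and the 95 at Harborview are included, and use a divisor that matches.
- Report BUP and naloxone event rows as events per 30 observed days beside N. Leave unique-provider and X-waiver rows as counts, with a note that they do not scale with time.
- Where the compiled dataset carries event dates, also show the two paused sites without the pause days.
- Treat a denominator of opioid-coded ED visits as optional, and use it only where numerator and denominator cover the same hours and dates.

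**Cost.** The first three items need wording, a few shell columns, confirmation of what was abstracted, and division of planned counts by days from dates already listed. Removing pause days, or recounting unique providers over equal 12-month windows, could need dated records or fresh abstraction, so neither should be a condition. The remaining weakness is that a per-time rate does not correct for changes in ED volume, and a footnote should say so.

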8.0 SAFETY ANALYSIS

Safety information for patient participants includes self-reported emergency department visits, hospitalizations, overdoses, and suicidal ideation, as well as deaths (not identified from a National Death Index search). Regardless of when the Day 30 follow-up visit occurs, deaths are only collected if the date of death occurred between the index ED visit and Study Day 30 (i.e., the safety window). This information will be summarized separately for those participants who were enrolled and later found to be ineligible. Note that deaths in the safety window are the only reportable adverse events.

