8.4 Secondary Effectiveness Outcome Measures

To compare the baseline evaluation and IF evaluation periods on:

1. Self-reported days of illicit opioid use (past 7 days) measured by TLFB methods at 30 days
2. Overdose events (past 30 days) captured by participant self-report, state medical examiner records, National Death Index and review of medical records
3. HIV risk taking behaviors (past 30 days) as measured by HIV Risk Taking Behavior Score
4. Healthcare service utilization (past 30 days) measured by Health Services Utilization Form
5. Rates of illicit opioid negative urines at 30 days

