10.2.20 Adverse Events (AEs) and Serious Adverse Events (SAEs)

All deaths, regardless of cause, will be captured for this study. These events may be identified when possible through using state medical examiner records, National Death Index, and review

of medical records. Appropriate information surrounding the event will be documented on the AE/SAE forms set. Only death events that occur within the 30 day follow-up period will be recorded on the AE/SAE form set.

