14.12 Adverse Events (AEs) and Serious Adverse Events (SAEs)

For the purposes of this protocol, the collection and reporting of safety events will be limited to hospitalization for all medical (including psychiatric) indications, Emergency Department visits, overdoses, and death of any participant enrolled in this study. The study staff will be trained to monitor for and report all protocol-defined safety events including Serious Adverse Events. All safety events, including designated SAEs will be presented to the DSMB. SAEs that are specified for reporting will be reported to the IRB of record per the IRB's guidelines.

Reportable AEs will include:

- None

Reportable SAEs will include:

- Any death for any reason

All deaths, regardless of cause, will be captured for this study. These events will be identified through the participants' locator information or when possible through using state medical examiner records, National Death Index, and review of medical records. Deaths will be reported using the Adverse Event/Serious Adverse Event form set so that appropriate information surrounding the event can be gathered. It is the expectation that all *deaths will be reported in the EDC within 24 hours of site awareness. *Note: only death events that occur within the 30-day follow-up period will be recorded on the AE/SAE form set.

OTHER SAFETY EVENTS OF INTEREST

Hospitalization for all medical (including psychiatric) indications, Emergency Department visits and overdose events will not be captured as AEs or SAEs, but instead will be reported on study specific form(s).

All hospitalization events (including psychiatric indications) as well as Emergency Department visits will be captured for this study using self-report as well as review of medical records. These hospitalizations will be reported on the Health Services Utilization and ED Visits and Hospitalization CRFs. When possible, these forms will confirm the diagnosis for the hospital or ED visit and the information will be verified by study staff. The completion of these forms will indicate whether the information was gathered via self-report or medical record abstraction. This information will be collected at enrollment and at the 30-day follow up visit.

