All overdose events will be captured for this study. Non-fatal overdose events will be captured through participant self-report on the Overdose CRF. This information will be collected at the enrollment visit as well as all follow-up visits for the study. Fatal overdose events will be captured through state medical examiner records, National Death Index, and review of medical records. *Fatal overdose events also qualify as a reportable SAE and will, therefore, be additionally reported on the AE/SAE CRF form set. *Note: only death events that occur within the 30-day follow-up period will be recorded on the AE/SAE form set.

OTHER EVENTS

Pregnancy is not exclusionary and will not be captured as the procedures for prescribing medication is per standard of care.

Incarceration that occurs on study will be reported on the Crime and Criminal Justice case report form but will not be considered an adverse or serious adverse event.

Loss of confidentiality related to participation in this study will be monitored at the site and will be reported on the Protocol Deviation eCRF as well as reported to the IRB of record per IRB requirements.

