3.3.5 Safety Window

As buprenorphine is an FDA approved marketed medication with known and labeled adverse events, safety events are only recorded on the AE/SAE form within the 30-day follow-up period and not followed to resolution. The safety window for this study is, generally, from 30 days prior to the index ED visit to Study Day 30. For ED visits and hospitalizations, suicidal ideation, and overdoses, the window is 30 days prior to the index ED visit for baseline and from baseline to Study Day 30 for the follow-up visit. Deaths occurring prior to Day 30, whether the site identifies on their own or the information was provided by NDI, are included. Should the site learn of a death (aside from NDI) after Study Day 30 and before the follow-up visit occurred, then this will be reported on the STC.

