IF Evaluation Period								

¹ Includes only deaths during 30-Day follow-up window, not those identified in NDI search.

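### The SAP both includes and excludes deaths found through the National Death Index, and it narrows the secondary overdose outcome to self-report without stating the departure from the protocol

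*SAP*

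**What the plan says.** **Deaths.** SAP 3.3.5 (Safety Window) states: "Deaths occurring prior to Day 30, whether the site identifies on their own or the information was provided by NDI, are included". SAP 8.0 (Safety Analysis) describes the safety data as self-reported events "as well as deaths (not identified from a National Death Index search". The footnote to the Listing 9 shell reads: "Includes only deaths during 30-Day follow-up window, not those identified in NDI search". SAP 8.4 lists and narrates deaths in the safety window and is silent on the NDI. Protocol 10.2.20 states: "All deaths, regardless of cause, will be captured for this study". Protocol 14.12 says deaths are identified through locator information or "when possible through using state medical examiner records, National Death Index, and review of medical records", and makes death the only reportable SAE.

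**Overdose.** Protocol 8.4 defines the secondary outcome as "Overdose events (past 30 days) captured by participant self-report, state medical examiner records, National Death Index and review of medical records". Protocol 12.13 and 12.14.4 repeat the four sources. Protocol 14.12 sends non-fatal overdoses to self-report on the Overdose form and says: "Fatal overdose events will be captured through state medical examiner records, National Death Index, and review of medical records". It adds: "Fatal overdose events also qualify as a reportable SAE and will, therefore, be additionally reported on the AE/SAE CRF form set". SAP 7.6.2 item 2 scores the outcome from question 1 of the overdose (ODE) form, a self-reported number of days. SAP 8.2 and Table 35 use the ODE form from the Day 30 visit. Table 35 has two day counts and no row for fatal overdose.

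**The concern.** Death is the one event this trial reports as an SAE, so the rule for which deaths are listed should have a single reading. Here a programmer following 3.3.5 and one following 8.0 would produce different Listing 9s whenever an NDI search found a death in the window that the site had not. The second programmer's version would leave that death out of safety reporting altogether.

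The overdose outcome has a related gap. The protocol hypothesis (4.3.4) is that patients in the IF evaluation period have fewer overdose events. As the SAP scores it, the comparison of periods cannot count a fatal overdose before Day 30, and the SAP does not say that this differs from the protocol definition. Where it departs from the protocol on the ChangeToOne policy (SAP 7.2.1), it says so and gives a reason.

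**Working it through.** The documents state no figure on this point, so the check sets the rules side by side.

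**Step 1: which deaths are listed.** Take a death between the index visit and Day 30.

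| How the death became known | SAP 3.3.5 | SAP 8.0 and Listing 9 footnote |
|---|---|---|
| Site identified it | included | included |
| NDI only | included | excluded |

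The rules differ in the second row. The footnote alone might be read as removing only NDI deaths outside the window. SAP 8.0 cannot be read that way: its exclusion carries no condition, and its next sentence sets the window separately.

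**Step 2: which overdose sources are used.**

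| Rule | Self-report | Medical examiner | NDI | Medical records |
|---|---|---|---|---|
| Protocol 8.4, 12.13, 12.14.4: outcome | yes | yes | yes | yes |
| Protocol 14.12: fatal overdoses | no | yes | yes | yes |
| SAP 7.6.2: outcome | yes | no | no | no |
| SAP 8.2, Table 35: summary | yes | no | no | no |

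The SAP keeps 1 of the 4 outcome sources and 0 of the 3 assigned to fatal overdoses.

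**Step 3: can a fatal overdose enter by self-report?** The follow-up visit falls on Day 30 or later (SAP 3.3.2; the Table 5 footnote gives days 30 to 44). A participant who dies before Day 30 cannot complete that form. The number of such deaths in the 7.6.2 outcome and in Table 35 is 0 by construction. The ODE form completed at enrolment feeds the baseline tables only.

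**Step 4: scale.** The documents give neither a 30-day fatal overdose risk nor the share of deaths known only through the NDI. As an illustration only, assume a risk of 0.1% to 1% in the planned 960 patients: 960 × 0.001 = 0.96 and 960 × 0.01 = 9.6 fatal overdoses left out of the overdose outcome. How many would also be missing from Listing 9 cannot be said.

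**Step 5: timing.** The last enrolment end date in SAP 3.3.6 is 4 October 2020. SAP 1.0 (14 June 2021) came 253 days later and SAP 2.0 (20 September 2021) 351 days later. The Revised SAP text changes only the primary models, leaves this point alone, and already reports a result (site-by-period interaction, p = 0.021).

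**The case against.** The strongest reply has four parts.

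- **The SAP is open about self-report.** This stands. SAP 7.6.2 names self-report and quotes the question, 8.0 calls the overdoses self-reported, and 8.2 names the form. A reader might infer that the restriction is concealed; the text does not support that. Only the Table 35 title lacks the word. What is missing is a statement that the measure is narrower than the protocol outcome.
- **Table 35 and Listing 9 follow the protocol's own split.** This largely stands. Protocol 14.12 sends non-fatal overdoses to the Overdose form and fatal ones to the AE/SAE forms, so the absence of deaths from Table 35 is not in itself a breach of 14.12. A reader might also infer that fatal overdoses vanish from all output. They do not: site-identified overdose deaths appear in Listing 9, which has a column for relation to overdose, and in the narratives. Site-known deaths also have a row in Table 5. The split does not excuse 7.6.2, because the outcome definition in protocol 8.4 covers all four sources.
- **NDI searching is only promised where possible.** That limits what will be found. It does not justify discarding what is found, and the SAP's list of forms includes an NDI form.
- **Little hangs on it.** No primary result is touched, and SAP 9.0 treats secondary findings as hypothesis-generating. That bears on weight. It does not settle which rule a programmer should follow for deaths.

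**Conclusion.** The point holds in two parts. First, SAP 3.3.5 contradicts SAP 8.0 and the Listing 9 footnote, and the exclusion runs against the protocol. Applied as written in 8.0, it would drop an NDI-only death in the window from every safety display. Second, SAP 7.6.2 reduces a four-source secondary outcome to one source without stating a departure, so neither that outcome nor Table 35 can contain a fatal overdose before Day 30.

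These conclusions rest on the text alone. The number of deaths affected cannot be derived, and whether any NDI-only death occurred is unknown. The documents do not show that the overdose comparison is biased towards either period. The correction is worth making because it is cheap and concerns the trial's only reportable SAE.

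**What to change.** **Deaths.** Delete the NDI exclusion in SAP 8.0 and in the Listing 9 footnote so that both agree with 3.3.5. List all deaths from the index visit to Study Day 30, with a column for source.

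**Overdose.** Title Table 35 'self-reported overdose days', and state in 7.6.2 that this measure is narrower than the protocol outcome. Beside it report, by period and over all participants in that period, (a) the number with a fatal overdose in the window, from the AE/SAE form or from the NDI form if that form gives cause of death, and (b) the number with no Day 30 ODE form. The second count is needed because the rule that treats missing data as failure (protocol 12.10, SAP 7.5.3) covers only the primary outcomes.

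**What not to do.** Do not add fatal events to the count model of self-reported days. With the protocol's offset for less than 30 days, a death on day 29 gives 1 ÷ (29/30) = 1.03 events per 30 days, while a survivor reporting 2 overdose days gives 2.00. The death would rank as the better result. On day 3 the same event gives 1 ÷ (3/30) = 10. The model would also assume no earlier overdose days in those who died, admit participants without a form only if they died, and still omit overdoses found in medical records.

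**Record.** Log the change in SAP 14.0 as post hoc, made after enrolment ended and after results were reported in the Revised SAP text.

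**Cost.** Wording and a little programming. The ODE, AE/SAE and NDI forms exist, and Listing 9 already carries relation to overdose. That the NDI form records cause of death is an assumption, since its fields are not shown.
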